8. Does the 17-OHPC concentration in maternal plasma or whole blood correlate better with certain pharmacological and clinical outcomes?

Subjects in the ancillary cohort will already be receiving 250 mg 17-OHPC weekly as part of their standard of care, based on their clinical history. The *primary objective* in the ancillary cohort is identical to the RCT.

The secondary research questions are similar to the RCT except for numbers 2, 3, and 7 above. Data will be collected from subjects in the ancillary cohort, but will not be utilized for secondary research questions 2 and 3 above. These research questions cannot be adequately addressed because subjects in the ancillary cohort are not randomized. Research questions 5 (cord blood only) and 7 cannot be addressed because biological fluids will not be collected at delivery in the ancillary cohort.

C.3. Screening Procedures

All patients who present for prenatal care before 20 6/7 weeks are eligible for screening. The latest gestational age to start treatment in the RCT is 21 6/7 weeks. Subjects who either refuse the RCT or are not approached may be eligible for participation in the ancillary cohort. The inclusion/exclusion criteria will be reviewed with the patient's chart. Potentially eligible subjects will be told about the study and asked to sign a medical records release so that the medical records of her previous deliveries may be obtained. Documentation of the previous deliveries will be reviewed to ensure the patient meets the inclusion criteria. If a patient appears to meet the criteria for enrollment and expresses interest in the study, she will be told about the study and asked to sign the informed consent form. A copy of the consent form will be provided to the patient.

C.3.i. Eligibility Criteria

a. RCT Eligibility Criteria

Inclusion Criteria - Subjects in the RCT must meet all of the following:

1. Pregnant female with documented prior birth between 16 0/7- 35 6/7 week gestation from spontaneous preterm labor or preterm premature rupture of membranes
2. Gestational age (GA) < 22 weeks, based on study determined GA (as treatment must start between 16 0/7 and 21 6/7 weeks)
3. Singleton gestation
4. Age between 18 – 45 years
5. Able to give informed consent and undergo study procedures

Exclusion Criteria - Subjects in the RCT must not meet any of the following:

1. Plan for cerclage
2. Plan for progesterone treatment other than study medication

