3. Known major fetal anomaly or chromosomal anomalies that might affect gestational age at delivery
4. Malformation of uterus (uterine didelphus, septate uterus or bicornuate uterus) or known cervical length <2.5 cm
5. Participation in another trial that may affect gestational age at delivery
6. Planned delivery at other institution where pregnancy outcome data cannot be obtained
7. Medical or obstetrical complication that might affect gestational age at delivery, such as active ulcerative colitis, liver tumors, liver disease/failure, renal disease/failure, undiagnosed vaginal bleeding unrelated to pregnancy, or hypertension requiring 2 or more agents
8. Current or history of thrombosis or thromboembolic disorders
9. Known or suspected breast cancer, other hormone-sensitive cancer, or a history of these conditions
10. Moderately severe depression (PHQ-9 score ≥15, EPDS score of >13, or suicidal ideation)

b. Ancillary Cohort Eligibility Criteria

Inclusion Criteria - Subjects in the ancillary cohort must meet all of the following:

1. Pregnant female with documented prior birth between 16 0/7- 35 6/7 week gestation from spontaneous preterm labor or preterm premature rupture of membranes
2. Receiving 250 mg 17-OHPC weekly- must be compliant with that treatment based on interview and reviewing the medical record
3. Gestational age (GA) <26 weeks, based on study determined GA

4. Singleton gestation
5. Age between 18 – 45 years
6. Able to give informed consent and undergo study procedures

Exclusion Criteria - Subjects in the ancillary cohort must not meet any of the following:

1. Inclusion in the RCT of 250 vs 500 mg OPRC study
2. Cerclage in place
3. Plan for progesterone treatment other than study medication
4. Known major fetal anomaly or chromosomal anomalies that might affect gestational age at delivery
5. Malformation of uterus (uterine didelphus, septate uterus or bicornuate uterus) or known cervical length <2.5 cm
6. Participation in another trial that may affect gestational age at delivery
7. Planned delivery at other institution where pregnancy outcome data cannot be obtained
8. Medical or obstetrical complication that might affect gestational age at delivery, such as active ulcerative colitis, liver tumors, liver disease/failure, renal disease/failure, undiagnosed vaginal bleeding unrelated to pregnancy, or hypertension requiring 2 or more agents
9. Current or history of thrombosis or thromboembolic disorder.

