At randomization, we will record height and weight from the medical record and collect information about demographics (e.g., age and race), social history (e.g., marital status, years of education, alcohol use, tobacco use and illicit drug use), medical and obstetric history, prenatal labs and ultrasound findings from the index pregnancy, and concomitant medication and supplement use. Self-reported information will be confirmed with the medical record. This visit is anticipated to last approximately 30 minutes.

C.6.iii. Study Visits

- **Randomized Clinical Trial:**

Each center will see subjects enrolled in the RCT every 6-9 weeks to provide additional medication and to perform other aspects of the study including examination of the injection sites, as needed. All subjects in the RCT will have venous blood draws performed at the times described in the protocol. Research staff will contact subjects weekly to record injection information, ask about possible side effects of the medication experienced since the last injection, and about the use of other medications. They will also ask about any hospitalizations and any pregnancy complications that have been diagnosed since the last contact. If complications of the pregnancy arise, such as need for a cervical cerclage, or need for vaginal progesterone, they will be recorded. If the patient is hospitalized for any reason including preterm labor, treatment should continue. The local principal investigator will evaluate the event's expectedness, relatedness and severity. Events will be reported to the local IRBs per institutional procedures and the participating investigators and FDA, as required. Details of monitoring, documenting and reporting serious adverse events (SAEs) will be documented in the study's safety monitoring plan. Weekly communication will occur until the patient delivers.

Subjects in the RCT will be assessed for depression using either the Patient Health Questionnaires (PHQ-2 and PHQ-9, if required) or the Edinburgh Postnatal Depression Scale (EPDS)⁴⁰ at the following study visits when maternal blood samples are collected: Screening Visit, 26-30 week visit, and 6-9 weeks after the 26-30 week visit.

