The Patient Health Questionnaire-2 (PHQ-2) will be administered as a screen for depression. If the PHQ-2 score is 3 or greater, major depressive disorder is possible and subjects will be further evaluated with the Patient Health Questionnaire-9 (PHQ-9). The PHQ-9 is a multipurpose instrument for screening, diagnosing, monitoring and measuring the severity of depression. Alternatively, the EPDS consists of 10 questions and is a valuable and efficient way of identifying patients at risk for perinatal depression.

- A PHQ-9 score of ≥ 15 or an EPDS score >13 represents moderately severe depression. Subjects with a PHQ-9 score of ≥ 15 or an EPDS score >13 at the Screening Visit will be excluded from enrolling in the study and will be referred to a mental health provider. Currently enrolled subjects who develop depression and have a PHQ-9 score

≥ 15 or an EPDS score >13 will not automatically be withdrawn from the study, but a risk-benefit discussion for 17-OHPC treatment is appropriate. Subjects will be offered a referral to a mental health provider, if not already in treatment. If the patient is in treatment, we will continue to monitor her depression and notify her treatment professional, as appropriate.

Note: Question 9 on the PHQ-9 and question 10 on the EPDS are single screening questions on suicide risk. If a subject answers yes to question 9 on the PHQ-9 or has a score ≥ 1 for question 10 on the EPDS, they are ineligible to continue with the study and will be immediately referred to a mental health provider for further assessment.

- A PHQ-9 score of ≥ 10 and < 15 or an EPDS score >10 and ≤ 13 indicates moderate depression. Subjects with moderate depression will not be excluded or withdrawn from the study, but a risk-benefit discussion for 17-OHPC treatment is appropriate. Patients will be offered a referral to a mental health provider, if not already in treatment. If the patient is in treatment, we will continue to monitor her depression and notify her treatment professional, as appropriate.

- **Ancillary Cohort:**

All subjects in the ancillary cohort will have venous blood draws performed at the times described in the protocol. Study drug will be dispensed to subjects during routine OB visits or during study visits. Subjects will be given enough medication to last 6-9 weeks. The administration of the injections will be managed by the prescribing physician.

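### In the RCT, women screened with the PHQ-2 who score 0–2 are never asked about suicide, although suicidal ideation is both an exclusion and a reason to stop treatment

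*Combined protocol and SAP*

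**What the plan says.** Section C.6.iii (Study Visits, Randomized Clinical Trial) has RCT women "assessed for depression using either the Patient Health Questionnaires (PHQ-2 and PHQ-9, if required) or the Edinburgh Postnatal Depression Scale". The assessments fall at the "Screening Visit, 26-30 week visit, and 6-9 weeks after the 26-30 week visit".

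The PHQ route has two steps: "If the PHQ-2 score is 3 or greater, major depressive disorder is possible and subjects will be further evaluated with the Patient Health Questionnaire-9". The EPDS is described as a ten-question instrument with no pre-screen.

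A note in the same section identifies the suicide items: "Question 9 on the PHQ-9 and question 10 on the EPDS are single screening questions on suicide risk". A woman who is positive on either one is handled without reference to her total score: "they are ineligible to continue with the study and will be immediately referred to a mental health provider for further assessment".

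Ideation also appears in two other places. RCT exclusion 10 in C.3.i reads "Moderately severe depression (PHQ-9 score ≥15, EPDS score of >13, or suicidal ideation", so ideation is an alternative to the score cut-offs. C.7.i(a) lists it among the reasons to stop 17-OHPC, with no score attached.

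**The concern.** The protocol attaches a decisive consequence to suicidal ideation. On one of its two permitted screening routes, however, it makes the only planned question about ideation depend on a short depression screen. A woman with ideation and a PHQ-2 of 0–2 could be enrolled, or could stay on treatment, without the referral the protocol intends, unless the ideation came to light some other way. Had she been given the EPDS, she would have been asked directly. Two women in the same condition can thus be handled differently because of the instrument used, and the protocol gives no rule for choosing between them.

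What is at stake is participant safety and uniform application of an eligibility rule.

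**Working it through.** The plan states no figure on this point, so there is nothing to reproduce. The check applies the C.6.iii rule to each route.

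**Inputs, all from C.6.iii**
- Planned assessments: 3.
- PHQ route: the PHQ-9, and with it question 9, is given only when the PHQ-2 is 3 or more. The complement is a score of 0–2.
- EPDS route: all ten questions are asked, so question 10 is always reached.
- Suicide items named: PHQ-9 question 9 and EPDS question 10, and no others.

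**Formula.** For a woman who attends all three assessments:
- EPDS route: suicide questions = 1 + 1 + 1 = 3.
- PHQ route: suicide questions = number of assessments with PHQ-2 of 3 or more.

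Each assessment is either 0–2 or at least 3, so there are 2 × 2 × 2 = 8 possible patterns.

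| Suicide questions asked | PHQ route, patterns | EPDS route, patterns |
|---|---|---|
| 0 of 3 | 1 | 0 |
| 1 of 3 | 3 | 0 |
| 2 of 3 | 3 | 0 |
| 3 of 3 | 1 | 8 |

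These are counts of patterns, not probabilities. On the PHQ route 7 of the 8 patterns leave at least one assessment without a suicide question. A woman scoring 0–2 throughout has 0 of 3, against 3 of 3 on the EPDS, a difference of 3 − 0 = 3.

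**Does another procedure fill the gap?**
- *Screening (C.3):* the eligibility criteria are checked against the chart. That is a record review, not a question to the woman.
- *Baseline (C.6.ii):* the listed data cover demographics, social, medical and obstetric history, laboratory and ultrasound findings, and medications. No suicide question is listed.
- *Weekly contact (C.6.iii):* staff record injections, "ask about possible side effects of the medication experienced since the last injection, and about the use of other medications", and ask about hospitalizations and pregnancy complications. Mood and suicide are not listed.
- *Stopping criteria (C.7.i):* the general safety clause lets staff act on ideation once it is known. It does not provide for asking.

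Any of these might bring ideation to light, but none is a planned question about it.

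**The case against.** Stepped screening is an explicit choice here, and the protocol nowhere promises to ask every woman about suicide. Exclusion 10 puts ideation inside the parenthesis that defines moderately severe depression, so it could be read as a marker of severe depression, to be sought only in women whose first screen suggests depression. C.7.i lists ideation beside drug allergy, thrombosis and cholestatic jaundice, and no screening test is scheduled for those either. The counts above restate the rule rather than measure harm. Extra positive screens would cost participants, and the planned 300 is only 300 − 296 = 4 above the requirement in D.2.

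Part of this stands. Listing ideation as a stopping criterion does not by itself oblige the study to ask everyone, and the practical size of the gap is unknown. The reading of ideation as a severity marker does not fit C.6.iii, though. There, an enrolled woman with a PHQ-9 of 15 or more, or an EPDS above 13, is not automatically withdrawn, whereas a woman with a positive suicide item cannot continue. The protocol thus treats ideation as more decisive than severity, and a rule that operates at any score needs a question asked at any score. Lost participants are a real cost, but each would be a woman the protocol already means to exclude or stop.

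C.6.iii also refers to a safety monitoring plan that is not among the documents. It is cited for serious adverse events, and nothing in the protocol suggests that it contains a suicide question, but that cannot be ruled out.

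**Conclusion.** The concern holds. Followed exactly, C.6.iii leaves an RCT woman on the PHQ route without a planned suicide question at every assessment where her PHQ-2 is 0–2: 0 of 3 if she scores 0–2 throughout, against 3 of 3 for any woman given the EPDS who attends all three.

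The conclusion rests on the written gate and on the two named items being the only planned ones. How many women with ideation would be missed cannot be computed. The documents do not give the share on each route, the proportion with a PHQ-2 of 3 or more, or the frequency of ideation among those scoring 0–2. No effect on the sample size or the primary analysis is claimed. The point is confined to the RCT; C.7.i states that its stopping rules do not apply to the ancillary cohort.

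**What to change.** Add one sentence to C.6.iii stating that, at each of the three assessments, PHQ-9 question 9 is put to every RCT woman on the PHQ route regardless of her PHQ-2 score. Alternatively, require the EPDS, which is already permitted, for all RCT women. Either change gives 3 of 3 planned suicide questions on every route.

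The first option adds one question for women scoring 0–2; the second replaces the short screen with ten questions. Both use existing visits and instruments already in the protocol. There may be additional positive screens, in a number the documents do not allow one to estimate. Each would need the referral already described and would make the woman ineligible to continue. C.7.i already provides for recruiting further subjects when treatment stops, so the planned sample can be kept at the price of that recruitment.

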Research staff will contact subjects weekly to record injection information, ask about possible side effects of the medication experienced since the last injection, and about the use of other medications. They will also ask about any hospitalizations and any pregnancy complications that have been diagnosed since the last contact. If complications of the pregnancy arise, such as need for a cervical cerclage, or need for vaginal progesterone, they will be recorded.

C.6.iv. Delivery

At delivery, pregnancy and neonatal outcome information will be obtained from the medical record. Biological samples will not be collected at delivery for subjects in the ancillary cohort.

C.6.v. Specimen Collection

a. RCT Specimen Collection

Maternal blood will be collected on four occasions by a health care provider or research staff trained in phlebotomy:

1. Prior to the 2nd injection (1 tube of 7 ml), ideally on day 7 from the first injection
2. Between 26-30 weeks - but only after a minimum of 7 injections have been administered (1 tube of 7 ml will be drawn just prior to the next injection; this will be a trough level)
3. Between 6-9 weeks after the 26-30 week specimen but not later than 37 weeks (1 tube of 7 ml will be drawn just prior to the next injection; this will be a trough level)
4. At delivery (1 tube of 7 ml), when possible

A second tube of blood (7 mL) will be drawn with any of the first 3 blood draws for genotyping of various genes related to preterm birth if mother consents to this optional test.

Umbilical cord blood (7 mL) will be collected at delivery. A second cord blood specimen (7 ml) will be drawn for genetics studies in the baby if mother consents. These blood specimens will be collected, when possible, and used to determine the concentrations of various biochemicals, 17-OHPC and its metabolites, and for genetic studies.

A 3 x 3 cm piece of placenta will be collected, when possible, for p-glycoprotein and other transporters.

Labor and Delivery biological specimens will be collected when possible. All biological specimens will be frozen at -70 to -80° C and stored locally until assayed at the University of Pittsburgh.

b. Ancillary Cohort Specimen Collection

Maternal blood will be collected on two occasions by a health care provider or research staff trained in phlebotomy:

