1. Between 26-30 weeks - but only after a minimum of 7 injections have been administered (1 tube of 7 ml will be drawn just prior to the next injection; this will be a trough level)
2. Between 6-9 weeks after the 26-30 week specimen but not later than 37 weeks (1 tube of 7 ml will be drawn just prior to the next injection; this will be a trough level)

A second tube of blood (7 mL) will be drawn with any of the first 2 blood draws for genotyping of various genes related to preterm birth if mother consents to this optional test.

C.7. Patient Management

No attempt will be made to alter or mandate clinical management of the subjects.

C.7.i Criteria for Stopping Treatment

In the event that either of the two scenarios below occur, treatment with 17-OHPC will stop and the subject will be retained in the study but their data related to 17-OHPC concentration will not be utilized since they will have stopped the medication. Additional subjects will be recruited to maintain the sample size.

- a. Systemic drug allergy, thrombosis during pregnancy, cholestatic jaundice, suicidal ideation, or other concern regarding the patient's safety
- b. Pregnancy termination (not planned at the time of eligibility determination)

The ancillary cohort is an observational cohort. This section is not applicable to the ancillary cohort, as the 17-OHPC medication is prescribed and managed by the subject's healthcare provider.

C.7.ii Non-Compliant Subjects

Compliance with drug administration will be documented by discussion with the subject during the weekly contact with the subject and by counting the used vials. Non-compliant subjects will be retained in the study and treatment with the randomized dose of 17-OHPC will continue; however, their data related to 17-OHPC concentration will not be utilized for the primary outcome. Additional subjects will be recruited to maintain the sample size. Non-compliance will be defined as:

- a. Subjects who miss any injections in the 4 weeks preceding the 26-30 week blood draw.
- b. Subjects who, after enrollment, admit to missing 2 or more injections after the first injection.

C.7.iii Subjects that Withdraw from the Study

If a subject in the RCT withdraws their consent, we will continue to provide the standard dose of 250 mg until treatment can be transitioned to the patient's healthcare provider, if desired, to ensure there is no lapse in patient care. Additional subjects will be recruited to maintain the sample size.

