We will also compare preterm birth rates between treatment groups (250 or 500 mg). Descriptive statistics will be generated for key characteristics of the treatment groups at baseline. For continuous variables, we will report means and standard deviations or medians and interquartile ranges (the latter in the case of skewed distributions or large outliers). Counts and percentages will be reported for categorical variables. We will then construct a Cox model and produce adjusted survival curves to assess the magnitude of differences in PTB rate

between groups while adjusting for covariates that may influence treatment effectiveness (e.g., BMI, race, gestational age at study entry).

We have previously performed population pharmacokinetic analysis of 17-OHPC in twin and singleton pregnancies. In this study, we will also use population pharmacokinetic analysis to evaluate the contribution of various covariates to the observed variability in the trough plasma concentrations of 17-OHPC, a surrogate measure of drug exposure.

D.2. Sample Size and Power

A Cox proportional hazards regression model will be used to assess the effect of log-transformed 17-OHPC concentration on event-free survival, while adjusting for covariates such as maternal BMI.

The recruited cohort of women will be sufficiently large to provide a wide range of drug exposures and enable evaluation of several potential covariates on plasma concentration of 17-OHPC and to describe the association between plasma concentration of 17-OHPC and its efficacy. Based on the large variation in 17-OHPC concentrations we have reported in clinical trials with the standard dose, we are confident that the range of concentrations of 17- OHPC that will be achieved with the two doses selected will provide a sufficiently wide range (between 4 and 112 ng/ml) to enable the performance of a robust concentration response assessment (Figure 7). Based on these simulated data, we estimate that 99% of subjects will achieve a concentration > 10 ng/ml with the 500 mg/week dose.

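### The protocol gives two different rules for a randomised woman who screens positive for suicide risk: leave the study (C.6.iii Note), or stop 17-OHPC and stay in it (C.7.i)

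*Combined protocol and SAP*

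**What the plan says.** Section C.6.iii sets the depression screens for RCT subjects at three times: "Screening Visit, 26-30 week visit, and 6-9 weeks after the 26-30 week visit". The Note in the same section concerns question 9 of the PHQ-9 and question 10 of the EPDS. For a subject who answers yes to the first, or scores 1 or more on the second, it says "they are ineligible to continue with the study and will be immediately referred to a mental health provider".

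Section C.7.i covers stopping treatment. Its first scenario includes "cholestatic jaundice, suicidal ideation, or other concern regarding" the patient's safety. The consequence is that "treatment with 17-OHPC will stop and the subject will be retained in the study". Her concentration data are set aside and a replacement is recruited.

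For follow-up in general, C.6.iii says "Weekly communication will occur until the patient delivers", and C.6.iv says that "pregnancy and neonatal outcome information will be obtained from the medical record".

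**The concern.** Two sections in force give different instructions for what is, in practice, nearly the same finding in a randomised woman. Under one she leaves the study. Under the other she leaves only the drug.

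What is at stake is follow-up, not treatment, since 17-OHPC stops on either reading. Section D.1 plans to compare preterm birth between the 250 mg and 500 mg groups, and lists maternal side effects and neonatal complications by dose as secondary outcomes. Section C.8 notes that the 500 mg dose is not FDA approved, so complete safety follow-up by dose matters. If a site ended participation on the strength of the Note, the loss would be triggered by a safety event and so could not be treated as random.

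**Working it through.** **Comparing the text**

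1. *Does the Note reach randomised women?* Yes. Two of the three screens follow randomisation. The bullet above the Note treats women at the Screening Visit and women already enrolled separately, but the Note makes no such distinction, and its wording about continuing fits someone already in the study.
2. *Could the Note mean the study drug only?* Perhaps, but it does not say so. The neighbouring bullets on depression scores speak of withdrawal from the study and, separately, of a risk-benefit discussion about 17-OHPC treatment. A coordinator therefore has reason to read the word study literally.
3. *Does C.7 provide for a woman removed under the Note?* No. C.7.i is stopped treatment with retention, and C.7.ii is non-compliance. C.7.iii is withdrawal: of consent in the RCT, with a separate paragraph for the ancillary cohort. A site that handled her under C.7.iii would find "If a subject in the RCT withdraws their consent, we will continue to provide the standard dose of 250 mg", whereas C.7.i requires the drug to stop. C.7.iii is limited to consent withdrawal in the RCT, so this is a risk of misrouting and not a stated rule.
4. *Does D.2 settle it?* No. D.2 keeps the outcomes of women who stop for drug allergy, thrombosis or cholestatic jaundice. It does not mention suicidal ideation.
5. *Where is there no conflict?* At the Screening Visit, where suicidal ideation is an exclusion criterion (C.3.i), and in the ancillary cohort, to which C.7.i does not apply.

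**Size per woman removed**

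The plan gives no figure to reproduce and no expected number of positive screens, so none is assumed. Inputs: 300 RCT women at 2:1 (C.2), hence n = 200 on 500 mg and n = 100 on 250 mg; preterm birth rate p = 0.28 in both arms (D.2).

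- Standard error of the dose difference: √[0.28 × 0.72 × (1/200 + 1/100)] = √0.003024 = 0.055, or 5.5 percentage points.
- One woman removed from the 500 mg arm: if she delivered preterm, 55/199 − 0.28 = −0.36 points; if at term, 56/199 − 0.28 = +0.14 points. The larger is 0.07 standard errors.
- One woman removed from the 250 mg arm: if she delivered preterm, 27/99 − 0.28 = −0.73 points; if at term, 28/99 − 0.28 = +0.28 points. The larger is 0.13 standard errors.
- Removing k women who all delivered preterm lowers the arm's rate by 0.72k/(n − k). To reach 0.055 takes k = 15 on 500 mg (10.8/185 = 0.058; k = 14 gives 0.054) or k = 8 on 250 mg (5.76/92 = 0.063; k = 7 gives 0.054).

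This is a crude bound on a difference of proportions. The planned dose comparison is an adjusted Cox model, and replacement recruitment is ignored.

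**The case against.** The best reply is that the intended rule can be recovered. C.7.i is the section on stopping treatment, it names suicidal ideation, and it spells out the consequence. The Note sits among questionnaire instructions, and its practical step is referral for assessment. The version history points the same way on intent: version 2.8 folded the former section on removing subjects or stopping treatment into C.7, and version 3.0 added the depression screens to C.6.iii and suicidal ideation to C.7.i together. Weekly contact to delivery and record-based outcomes also fit retention. I accept that retention is probably meant. But no sentence gives C.7.i precedence, and the Note says otherwise.

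A second reply is that the triggers differ: a positive answer to one screening question is not yet established suicidal ideation. That is fair, and the two events overlap without being identical. It does not help the plan, however, because the milder trigger would then carry the harsher consequence.

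A third is that the harm is conjectural. That stands. Nothing says data collection ends for such a woman. Serious adverse event handling is in a separate safety monitoring plan, so any effect on DMC review cannot be judged from these documents.

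**Conclusion.** The inconsistency is real and minor. As written, the Note is wrong for randomised women if C.7.i states the intended rule, which is the more plausible reading.

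The primary concentration analysis is little affected, because C.7.i already sets these women's concentration data aside. For the dose comparison, the shift is at most 0.07 (500 mg) or 0.13 (250 mg) standard errors per woman removed, assuming the planned 2:1 split and a 28% preterm rate in both arms. The number of women is unknown and probably small. The reason to correct the text is that sites should have one instruction after a suicide-risk finding, and that instruction should not cost safety follow-up.

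**What to change.** Split the C.6.iii Note in two:

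- **At the Screening Visit:** a woman with a positive item is not enrolled and is referred.
- **After randomisation:** she is ineligible to continue study treatment, is referred at once, and is retained under C.7.i, with weekly contact and with delivery and safety outcomes collected unless she withdraws consent.

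Optionally, and as a separate tidy-up, add suicidal ideation and other safety concerns to the D.2 list of treatment stoppers whose outcomes are kept. Leave pregnancy termination out of that edit unless its handling as an outcome is also specified.

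The cost is a wording change to one Note, plus two items on an existing list if the optional edit is made. Weekly contact and record-based delivery outcomes are already planned, so there is no new data collection.
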